### **9.2.3 Low Level Risks**

Low Level Risk does not indicate the likelihood the event will occur but indicates per the RACT assessment that no new or complex procedures are needed to ensure screening is adequate to eliminate or manage the risk in the patient population.

#### **9.2.3.1 Thermoregulatory Risks and Mitigation**

MDMA administered in a controlled setting produces only a slight increase in body temperature [114]. Ambient temperature does not enhance or attenuate this slight elevation in humans. In data gathered from sponsor-supported Phase 2 and Phase 3 studies, it was found that compared to placebo, a higher percentage of participants receiving MDMA had peak body temperatures greater than 1 degree Celsius (° C) above Baseline. However, there was no strong relationship between dose of MDMA and peak body temperature or between MDMA dose and elevation above threshold of 1° C above Baseline.

Ambient temperature should be kept at a comfortable level during Experimental Sessions. If a participant's temperature rises more than 1° C or the participant states that they feel hot, attempts should be made to decrease body temperature and increase comfort by removing blankets and layers of clothing, decreasing the ambient temperature, and, if necessary, directing a fan toward the participant. If at any time the temperature rises more than 1.5° C above Baseline despite these efforts, the site physician should be consulted for further evaluation and treatment.

#### **9.2.3.2 Osmoregulatory Risk and Mitigation**

MDMA administered in a controlled setting is not expected to have any risks of osmoregulatory changes. Participants are not allowed to drink more than three liters of water over the course of the Experimental Session and fluid intake will be spread out appropriately during the session. If a participant exhibits any signs of toxicity or clinically significant dilutional hyponatremia despite these precautions after an Experimental Session, they should not receive another Experimental Session unless it is approved by the investigator, site physician, and the Medical Monitor.

#### **9.2.3.3 Genotoxicity Risk and Mitigation**

The standard genotoxicity battery for MDMA has demonstrated that MDMA is negative for in vitro and in vivo genotoxicity, both with and without metabolic activation.

#### **9.2.3.4 Reproductive and Developmental Risks and Mitigation**

There are no data from the use of MDMA in pregnant women. In the absence of these data, epidemiological studies of Ecstasy are the only source of human data. One of two studies of Ecstasy users suggests that use of Ecstasy and polydrug use during pregnancy may be associated with some abnormalities at birth while the other failed to find this association [115, 116].

Studies in rats and rabbits have not shown direct or indirect harmful effects with respect to reproductive toxicity. Repeated dose toxicity studies of adequate duration, fertility, early embryonic development, and embryofetal development studies of MDMA with toxicokinetics have been completed. These studies established the “no-observed-adverse-effect level” (NOAEL) dose to be excluded the highest dose level evaluated at  $\leq 10$  mg/kg/day (supratherapeutic dose) in both sexes of the rat for fertility, reproductive performance, and for maternal and developmental toxicity in the rabbit. The NOAEL dose was the highest dose level evaluated at  $\leq 15$  mg/kg/day (supratherapeutic dose) for maternal and developmental toxicity in the rat. Due to the short half-life and single-dose dosing regimen of MDMA, pre- and post-natal development studies are not considered necessary for assessment of risk to the unborn. Assessment of embryofetal risk based on all available non-clinical and clinical data supports unlikely human teratogenicity/fetotoxicity in early pregnancy. On the basis of male fertility studies, the embryofetal risk posed from treatment of male participants with MDMA is also unlikely.

People who are able to become pregnant are included in the studies in this program, defined as those who are fertile, following menarche and until becoming post-menopausal unless permanently sterile. Permanent sterilization methods include hysterectomy, bilateral salpingectomy and bilateral oophorectomy. Postmenopausal state is defined as no menses for 12 months without an alternative medical cause. As a precautionary measure in clinical trials, participants who are able to become pregnant must have a negative pregnancy screen before undergoing each Experimental Session, which are conducted in monthly intervals, and must agree to use adequate contraception at least for the duration of the study during the Treatment Period which is 10 days post the last dose of MDMA. The end of relevant systemic exposure to MDMA is approximately 48 hours [117].

## 9.2.4 Minimal Risks

Minimum Level Risk does not indicate the likelihood the event will occur but indicates per the RACT assessment that no procedures are needed beyond basic monitoring to ensure screening is adequate to eliminate or manage the risk in the patient population.

### 9.2.4.1 Common Expected AEs

Common expected AEs were typically observed during Experimental Sessions, but were transient and typically diminished as the MDMA was metabolized and excreted over the next 72 hours after dosing. In the Phase 3 study MAPP1, the most common adverse events reported more frequently reported in the MDMA group were muscle tightness, decreased appetite, dizziness, nausea, hyperhidrosis, feeling cold, restlessness, mydriasis, dizziness (postural), bruxism, nystagmus, increased blood pressure, feeling jittery, chest pain (non-cardiac), dry mouth, vision blurred, pollakiuria, intrusive thoughts, vomiting, stress, and musculoskeletal chest pain. AEs were typically self-limiting.

### 9.2.4.2 Neurotoxicity Risk

It does not appear that MDMA-assisted therapy negatively impacts cognitive function based on data from Phase 2 studies sponsored by MAPS. The sponsor has carefully considered the risks of such neurotoxicity and conclude that they are minimal in the proposed study. This conclusion is supported by empirical and toxicokinetic evidence and is consistent with the lack of toxicity reported in previous clinical MDMA studies.

### **9.2.4.3 Abuse Potential**

Despite its classification as a Schedule I drug, an examination of findings in humans and animals suggests that MDMA possesses moderate abuse potential that is higher than that reported for “classic hallucinogens” like psilocybin, but lower than that reported for psychostimulants, such as cocaine or methamphetamine. There have been no AESIs reported in Phase 2 and Phase 3 studies that could be suggestive of abuse potential among research study participants treated with MDMA. Diversion is not an issue for sponsor-supported studies because MDMA is only administered under the supervision of the clinical investigator and no take-home doses are permitted. MDMA administration and handling follows all regulations pertaining to the use of controlled substances within research studies.

Studies assessing prevalence of problematic Ecstasy use or dependence suggest that a small percentage of individuals, especially those with prior psychological difficulties, may develop problematic Ecstasy use or dependence. An observational long-term follow-up assessment conducted at least 12 months after participation in a MAPS-sponsored early Phase 2 PTSD study of MDMA-assisted therapy found that 8.7% (8 of 92) participants reported using Ecstasy subsequent to study participation, with 6 of these 8 participants having used Ecstasy prior to study enrollment. Several participants volunteered that they would not seek out MDMA outside of a psychotherapeutic setting.

## **10.0 Safety**

### **10.1 Adverse Events**

In accordance with guidance for the specific study site, FDA Safety Reporting Requirements for INDs and BA/BE Studies, an Adverse Event (AE) is defined as any medical occurrence in a participant, including any abnormal sign (e.g., abnormal physical exam or laboratory finding), symptom, or disease, temporally associated with the participant’s involvement in the research, whether or not considered related to participation in the research. This definition includes concurrent illnesses or injuries and exacerbation of pre-existing conditions.

Events related to planned treatments or physician visits for Baseline conditions collected in the medical history will not be collected, unless there is an exacerbation of the condition, in which case they will be actively followed until resolution.

An unexpected AE is one that is not listed in the current IB or an event that is by nature more specific or more severe than a listed event.

The site physician will be responsible for reviewing and confirming all AEs and SAEs collected during the study. The therapy pairs will collect AEs during study visits from Enrollment (Visit 0) through Study Termination. Participants will be asked directly how they are feeling during each contact, and AEs may be captured spontaneously during therapy sessions, telephone calls, or other correspondence. Completed measures may create suspicion that an AE occurred; in this case, the site staff should follow-up with the participant.

All AEs will be monitored by the therapy pair until resolution or, if the AE becomes chronic, a cause can be identified. If an AE is unresolved when a participant terminates from the study, a clinical assessment will be made by the site physician, investigator, and/or Medical Monitor as to whether continued follow-up of the AE is warranted.

The severity of events reported on the “Adverse Events” eCRF will be determined by the site physician as:

- Mild: No limitation in normal daily activity
- Moderate: Some limitation in normal daily activity
- Severe: Unable to perform normal daily activity

The seriousness and relationship of study treatment to an AE will be determined by the Investigator based on the following definitions:

1. “Not Related”: The AE is not related if exposure to the investigational product has not occurred, or the occurrence of the AE is not reasonably related in time, or the AE is considered unlikely to be related to use of the investigational product, i.e., there are no facts (evidence) or arguments to suggest a causal relationship, or the AE is more likely related to the subject’s pre-existing condition.
2. “Related”: The administration of the investigational product and AE are considered reasonably related in time and the investigational product is more likely than other causes to be responsible for the AE or is the most likely cause of the AE.

### **10.1.1 Adverse Events of Special Interest**

In accordance with the guidance Clinical Safety Data Management Definitions and Standards for Expedited Reporting ICH Topic E2A: Guidance for Industry or FDA Safety Reporting Requirements for INDs and BA/BE Studies, the sponsor will pay special attention to a subset of AEs. These AEs will be marked in the eCRF with the denotation “Adverse Event of Special Interest” (AESIs) whether serious or non-serious.

In order to assess signals of cardiovascular risk for the IMP in the intended patient population that could be indicative of QT interval prolongation or cardiac arrhythmias, including Torsade de pointes, sudden death, ventricular extrasystoles, ventricular tachycardia, ventricular fibrillation and flutter, non-postural syncope, and seizures.

The subset of AEs involving suicide risk under the following terms are also of special interest:

- Suicides
- Suicide attempts
- Self-injurious behavior associated with suicidal ideation
- Suicidal ideation scores of 4 or 5 on the C-SSRS
- Suicidal ideation judged to be serious or severe in the opinion of the investigator

These AEs will be marked in the eCRF with the denotation “Adverse Event of Special Interest” (AESIs) whether serious or non-serious.

In order to assess signals of abuse potential for the IMP in the intended patient population:

- AESIs involving the terms of Behavioral addiction, Drug abuser, Substance abuser, Dependence, Intentional product misuse, Overdose (accidental, intentional, or prescribed), or Drug diversion in cases that are related to MDMA or “Ecstasy” (material presented as MDMA) will be collected and coded as AESIs in the eCRF.
- Cases of noncompliance, protocol violations, participants lost to follow-up, and any other reasons why participants dropped out of the study will be assessed for presence of AESIs;

- Qualitative urine drug test data will be collected prior to each Experimental Session. Any positive findings that cannot be attributed to pre-approved concomitant medications or diet will be reviewed by the Medical Monitor to assess compliance with ongoing eligibility criteria and for presence of AESIs.

If an AESI is a SAE or if it involves suicide risk, it should be reported via the eCRF within 24 hours of the site's awareness of the event.

### **10.1.2 Serious Adverse Events**

In accordance with guidance Clinical Safety Data Management Definitions and Standards for Expedited Reporting ICH Topic E2A: Guidance for Industry or FDA Safety Reporting Requirements for INDs and BA/BE Studies, an SAE is defined as any untoward medical occurrence that at any dose:

- Results in death.
- Is life-threatening (i.e., the participant was, in the opinion of the investigator, at immediate risk of death from the event as it occurred); it does not refer to an event which hypothetically might have caused death if it were more severe.
- Requires or prolongs inpatient hospitalization.
- Results in persistent or significant disability/incapacity (i.e., the event causes substantial disruption of a person's ability to conduct normal life functions).
- Results in a congenital anomaly/birth defect.
- Requires intervention to prevent permanent impairment or damage.
- Is an important and significant medical event that may not be immediately life-threatening or resulting in death or hospitalization, but based upon appropriate medical judgment, may jeopardize the participant or may require intervention to prevent one of the other outcomes listed above.

AEs which do not fall into these categories are defined as non-serious. It should be noted that a severe Adverse Event need not be serious in nature and that a SAE need not, by definition, be severe.

In addition, a pre-existing event or condition that results in hospitalization should be recorded on the medical history. The hospitalization would not result in the event or condition being reported as a study-related SAE, unless, in the view of the site physician, hospitalization was prolonged as a result of participation in the clinical trial or was necessary due to a worsening of the pre-existing condition. This is because the onset of the event (the reason for the procedure) occurred before the participant was entered in the trial. Hospitalization for cosmetics, non-emergency prophylaxis, or elective abortion does not result in an SAE report, unless, in the view of the site physician, hospitalization for these procedures was prolonged as a result of participation in the clinical trial.

All SAEs will be collected from the time of informed consent through Study Termination. All SAEs which occur during the course of the trial, whether considered to be associated with IMP or not, must be reported to the sponsor within 24 hours of the site staff's awareness of occurrence. Reporting procedures will be provided to the site. All SAEs will be assessed for relationship, expectedness and any required actions to address safety at the time of reporting of the event. SAEs will be evaluated by the site physician and Medical Monitor to determine if it is appropriate for the participant to continue treatment or enter follow-up. Any participant who experiences a SAE considered related to the IMP administration will be permanently discontinued from future IMP treatments

## 10.2 Other Significant Events

Significant life events that may occur during the course of the study, including death of a loved one, loss of employment, or other hardship, may have an impact on treatment outcome. The sponsor will capture these life events using the LEC-5 measure. Such events will be entered as Comments in the eCRF and if appropriate, described in the Case Study Report for data outliers, if any.

## 10.3 Pregnancy

### 10.3.1 Definition of ‘Able to Become Pregnant’

A participant is considered able to become pregnant if they were assigned female at birth and are post-menarche. A participant is considered not able to become pregnant if they are premenarchal, surgically sterile (documented hysterectomy, bilateral salpingectomy, bilateral oophorectomy, and/or tubal ligation), postmenopausal, or assigned male at birth.

### 10.3.2 Contraception Guidelines

Study participants who were assigned male at birth with partners who are able to become pregnant will not be required to practice contraception. Adequate contraception is required for all participants of who are able to become pregnant, regardless of sexual activity, sexual orientation, or the sex of their partner. Abstinence from penile-vaginal intercourse is not an adequate contraception plan by itself; participants must agree to a back-up method (e.g., condoms with spermicide) if they do choose to engage in penile-vaginal intercourse. It is recommended to stock condoms with spermicide at the study site to provide to participants if they need them. Adequate contraception methods include:

- Intrauterine device (IUD)
- Intrauterine hormone-releasing system (IUS)
- Non-oral hormonal methods, including injected, intravaginal, implanted, transdermal
- Oral hormones plus a barrier contraception (condom, diaphragm, or spermicide)
- Double barrier method (at least two of the following: condom, diaphragm, and spermicide)
- Vasectomized sole partner

For questions about acceptable contraception methods, contact the Medical Monitor.

### 10.3.3 Follow-up Requirements

Details of all pregnancies in study participants will be collected after Enrollment (Visit 0) and collected through 10 days after the last Experimental Session. Pregnancies should be reported to the sponsor via telephone or email within 24 hours of site staff awareness.

In the event of a pregnancy, the participant will discontinue Experimental Sessions but may continue with non-drug Integrative Sessions, the next CAPS-5 assessment, and Study Termination procedures. At a minimum, prior to withdrawal from the study, efforts should be made to assess the final CAPS-5 immediately and complete Study Termination procedures. The participant will be emergency unblinded if the participant wishes as described in [Section 8.4 Blinding and Bias Minimization](#), after the final CAPS-5 assessment.

The investigator will collect follow-up information on the participant and neonate and forward to the sponsor until the outcome of the pregnancy, which will be reported on an optional Pregnancy eCRF. Any termination, elective or spontaneous, will be reported. Abnormal pregnancy outcomes, such as spontaneous abortion, fetal death, stillbirth, congenital abnormalities, or ectopic pregnancy, will be reported as SAEs.

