## 3.0 Eligibility Criteria

### 3.1 Inclusion Criteria

At the completion of Screening, participants must meet all eligibility criteria and agree to all lifestyle modifications to be enrolled. Each participant will then enter the Preparatory Period which includes medication tapering, if needed, and non-drug Preparatory Sessions. The Preparatory Period ends with Enrollment Confirmation. A participant's enrollment will be confirmed if they have completed medication tapering, have a confirmed PTSD diagnosis per the CAPS-5 assessment and a Total Severity Score of 28 or greater, a total PCL-5 score of 36 or greater at Screening, continue to agree to all lifestyle modifications, and continue to meet all eligibility criteria (those criteria marked with an \* below will only be assessed at Screening, since they will not change).

Potential participants are eligible to enroll in the protocol if they:

1. \*Are a U.S. military veteran at least 18 years old
2. \*Are able to provide written, informed consent
3. \*Are able to swallow pills
4. Agree to have study visits recorded, including Experimental Sessions, Independent Rater assessments, and non-drug therapy sessions

5. Must provide a contact (relative, spouse, close friend or other support person) who is willing and able to be reached by the investigators in the event of a participant becoming suicidal or unreachable
6. Must agree to inform the investigators within 48 hours of any medical conditions and procedures
7. If able to become pregnant, must have a negative pregnancy test at study entry and prior to each Experimental Session, and must agree to use adequate contraceptive methods through 10 days after the last Experimental Session. Adequate contraceptive methods include intrauterine device (IUD), injected, implanted, intravaginal, or transdermal hormonal methods, abstinence, oral hormones plus a barrier contraception, vasectomized sole partner, or double barrier contraception. Two forms of contraception are required with any barrier method or oral hormones (i.e., condom plus diaphragm, condom or diaphragm plus spermicide, oral hormonal contraceptives plus spermicide or condom). ‘Not able to become pregnant’ is defined as permanent sterilization, postmenopausal, or assigned male at birth

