#### **4.4.3 Early Termination from the Study**

Participants who are removed from the study after they are randomized and receive IMP but do not complete the study may fall into one of these categories: Post-randomization Early Termination or Dropout. If the participant has received IMP in at least one Experimental Session and completed one CAPS-5 assessment beyond Baseline, they will be considered evaluable. All participants who receive IMP in at least one Experimental Session will be included in all safety analyses.

Participants can withdraw from treatment or withdraw consent at any time for any reason without judgment. The site team can withdraw a participant if, in their clinical judgment, it is in the best interest of the participant or if the participant cannot comply with elements of the protocol that are critical for safety or for the scientific integrity of the study. If the site team makes the decision to terminate the participant from treatment or the study, they will explain the reason for withdrawal and document in the participant's source records and eCRF. If a participant develops any Exclusion Criteria that, in the opinion of the Medical Monitor or Site, affects the safety of the participant, including psychiatric diagnosis, medical diagnosis, pregnancy, or requiring use of prohibited medications, the participant will discontinue treatment in Experimental Sessions but remain in the study for the associated Integrative Sessions. Participants whose Experimental Sessions are delayed by the COVID-19 pandemic may start any of these medications during the delay, as clinically indicated. When study visits resume, they will be given the option to resume Experimental Sessions after tapering off of these medications per [Section 11.1 Tapering Instructions](#). Any time a participant terminates from the study early, the site team will attempt to obtain information about AE outcomes if appropriate, as determined by the site physician and Medical Monitor. The site team will provide the participant with a Post-Study Plan as described in [Section 7.4.3 Post-Study Plan](#).

- **Post-randomization Early Termination:** Participants who discontinue study treatment but continue to participate in Independent Rater primary and secondary outcome assessments. Data collection by IRs will continue on the same schedule as planned through Study Termination visit procedures.

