**Table 9: Schedule of Procedures for Experimental Sessions**

Approximate Time	Procedure or Action
8:30	Urine drug screen and pregnancy test, concomitant medication information collected, self-reported measures and C-SSRS administered, participant acclimated to environment
8:55	Baseline BP, body temperature, pulse
9:00	IMP Administration , Begin video recording
10:30	BP, body temperature pulse Supplemental Dose Administration , unless tolerability issues emerge with the first dose or it is refused by the participant
16:30	C-SSRS, BP, body temperature, pulse

*Pre-IMP Administration*

- 24 to 48 hours prior to the first Experimental Session, the participant will be randomized.
- On the day of the Experimental Session, the participant will arrive approximately 30 to 60 minutes prior to IMP administration.
- The therapy pair will direct the participant to complete the PCL-5 and BDI-II and will administer the C-SSRS.
- The site team will ensure the participant has not used caffeine or nicotine 2 hours prior and has fasted for 10 hours prior to IMP administration and complied with all other requirements per [Section 3.3 Lifestyle Modifications](#).
- The site team will inquire about any possible changes in health to ensure the participant continues to meet all eligibility requirements and record AEs as described in [Section 10.0 Safety](#).
- The site team will instruct the participant that they will not be able to use caffeine or nicotine at least 6 hours after the IMP administration.
- The site team will complete urine drug screen, pregnancy test, and concomitant medication review.
  - A positive drug screen will be reviewed by the site physician and may be cause for delaying IMP administration to a later time, rescheduling the session to a later date, or withdrawing the participant from the study, based on Medical Monitor review.
  - A positive pregnancy screen is cause for withdrawal from the protocol.
- The therapy pair will review procedures for the Experimental Session with the participant and discuss the participant's goals, intentions, and concerns and some of the commonly experienced effects of MDMA.
- If the participant continues to be eligible, the session will proceed.
- Baseline blood pressure, body temperature, and pulse will be measured just prior to administration of the initial dose.

*During the Experimental Session*

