## **11.0 Concomitant Medications**

### **11.1 Tapering Instructions**

The site physician will record concomitant medications during Screening. If the prospective participant is being treated with psychiatric medications at enrollment, the prospective participant will be encouraged to discuss medication tapering with their outside treating physician, if any, and will be required to give the site physician permission to do so as well. Additionally, participants who are taking prohibited opiates will be cross-tapered to an allowable opiate (hydrocodone, morphine, and codeine) under the care of their prescribing physician.

The site physician will consult the prescribing physician to initiate medication tapering for participants, as they must refrain from taking psychiatric medications throughout the study, with some exceptions (see [Section 11.2 Allowed Concomitant Medications](#)). The prescribing physician's opinion about medication discontinuation will be documented either in writing from the prescribing physician, or in writing by the site physician documenting phone contact with the prescribing physician. Tapering will follow a time course appropriate for the medication based on its half-life, with the Baseline CAPS-5 T1 (Visit 3) scheduled to occur after complete washout for psychological medications and Experimental Session 1 (Visit 5) scheduled to occur after complete washout for medications with drug-drug interactions without a psychological concern (five half-lives plus at least 1 week for stabilization).

The therapy pair will request information about any changes in medication at each contact. The site physician will be responsible for reviewing and confirming all medications collected during the study.

All medications, non-prescription and prescription, will be collected from Screening through 7 days after the last Experimental Session. From 7 days after the last Experimental Session through Study Termination, only prescription or non-prescription medications taken to treat AEs will be collected. Throughout the protocol, all medications used to treat AEs will be collected, and all changes including discontinuations or additions to medications will be collected. The study team will also inquire about concomitant medication adherence and document all information on the Concomitant Medications eCRF.

Participants may return to taking psychiatric medications and discontinue contraception after the final Study Termination visit if necessary.

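### Pregnancy collection is written to close 10 days after the last Experimental Session, with no later test, so capture of a pregnancy exposed to the last dose is uncertain; the rules on a positive test and on the end of contraception also conflict

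*Protocol*

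**What the plan says.** **Collection window.** Protocol Section 10.3.3: "Details of all pregnancies in study participants will be collected after Enrollment (Visit 0) and collected through 10 days after the last Experimental Session". The next sentence asks sites to report pregnancies to the sponsor within 24 hours of becoming aware of them and sets no end date. The section also requires follow-up of participant and neonate to the outcome of the pregnancy, and reporting of abnormal outcomes as SAEs.

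**Testing.** Section 9.2.3.4 says participants who can become pregnant "must have a negative pregnancy screen before undergoing each Experimental Session". Table 9 puts that test at 8:30, half an hour before dosing: "Urine drug screen and pregnancy test, concomitant medication information collected". Tables 5 and 6 mark a pregnancy screen at V5 and V9, and at V13 for the 3-session group. Nothing is marked after the last session, and Sections 7.4.1 and 7.4.2 list no later test.

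**Exposure.** Section 9.2.3.4: "The end of relevant systemic exposure to MDMA is approximately 48 hours". The same section says there are no data on MDMA use in pregnant women.

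**Other safety data.** AEs run from Visit 0 to Study Termination (Section 10.1). SAEs run from consent to Study Termination (Section 10.1.2).

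**After a positive test.** Section 7.3.1 (Pre-IMP Administration): "A positive pregnancy screen is cause for withdrawal from the protocol". Section 4.4.3, which names pregnancy among its examples, says "the participant will discontinue treatment in Experimental Sessions but remain in the study for the associated Integrative Sessions". Section 10.3.3 stops Experimental Sessions but allows the participant to go on with Integrative Sessions, the next CAPS-5 and termination procedures.

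**End of contraception.** Criterion 7 in Section 3.1: participants "must agree to use adequate contraceptive methods through 10 days after the last Experimental Session". Section 11.1: "Participants may return to taking psychiatric medications and discontinue contraception after the final Study Termination visit if necessary". The screening procedures in Section 7.1.1 describe a commitment for the whole study. Section 9.2.3.4 combines the study duration and the 10-day limit in one sentence.

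**The concern.** The contraception window and the pregnancy collection window end on the same day, which leaves no time for a pregnancy conceived near the end of the first to be recognised before the second closes. The pre-dose test cannot show a very recent conception, and no scheduled test follows it. Yet participants are still seen for at least another 40 days, and AEs and SAEs are collected throughout.

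At stake is a small but scarce kind of safety information. With no human pregnancy data on MDMA, each exposed pregnancy is informative, and the protocol wants it followed to outcome. A site applying the written window literally could learn of such a pregnancy at T2 or Study Termination and not record it. If the outcome then falls after Study Termination, the SAE route has closed as well.

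Separately, a site cannot follow both versions of the rule for a positive test, or both end dates for contraception.

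**Working it through.** The 10-day limit is a set rule with no derivation, so there is no plan figure to reproduce. The check is calendar arithmetic, with the last Experimental Session as day 0.

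**1. How long the study continues after collection closes**
- T2 is 49 to 56 days after the last session (Protocol Table 1). Gap after day 10: 49 − 10 = 39 to 56 − 10 = 46 days.
- 3-session group: Study Termination is 1 to 7 days after the final CAPS-5 (Section 7.4.2), so day 49 + 1 = 50 to 56 + 7 = 63. Gap: 40 to 53 days. The V18 and V19 windows in Table 5 allow up to 56 + 7 + 7 = day 70, a gap of 60 days.
- 2-session group: T2.2 is 28 to 35 days after T2, so day 77 to 91. Study Termination is then day 77 + 1 = 78 to 91 + 7 = 98. Gap: 68 to 88 days.

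**2. Which conceptions count as exposed**
- The half-life is 7 to 9 hours (Section 1.2.2). Five half-lives are 5 × 7 = 35 to 5 × 9 = 45 hours, in line with the stated 48 hours. The latest exposed conception is taken as day +2.

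**3. Which conceptions are recognised in time**
- Let c be the day of conception and L the lag to recognition. L is not in the documents; it is assumed to be 10 to 28 days.
- A pregnancy is inside the written window only if c + L ≤ 10, that is, c ≤ 10 − L. The latest conception day caught is 0 at L = 10, −4 at L = 14, −11 at L = 21 and −18 at L = 28.
- For conceptions on day 0 to +2, any lag over 10 days puts all of them outside the window.

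**4. Share recognised late**
- Assume that the pre-dose test misses conceptions less than L days old and that conception dates are uniform. Exposed pregnancies not detected at the last test then span day −L to +2, a length of L + 2.
- Those recognised after day 10 span day 10 − L to +2, a length of L − 8.
- Share late = (L − 8)/(L + 2).

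| L (days, assumed) | Share recognised after day 10 |
|---|---|
| 10 | 2/12 = 17% |
| 14 | 6/16 = 38% |
| 21 | 13/23 = 57% |
| 28 | 20/30 = 67% |

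The share passes one half when 2(L − 8) > L + 2, that is, when L > 18.

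The model uses one lag for both the urine test and later recognition. Separating the two could move the share either way, so the percentages only illustrate the size.

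**The case against.** The strongest reply is that the protocol has other routes. The 24-hour reporting rule in Section 10.3.3 has no end date. Criterion 6 requires participants to tell investigators of medical conditions within 48 hours, also with no stated end. Telephone calls continue to day 14 (Section 7.3.2), and the outcome site visit and Study Termination ask about health or AEs. Abnormal outcomes known before Study Termination would be SAEs. The window sentence can also be read as covering pregnancies that begin by day 10, whenever they are learned of. All of this stands, and it is why capture is uncertain rather than excluded. It does not remove the problem: the window and the reporting rule sit side by side in one section and can lead sites to different practice.

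A reader might infer three stronger things, and the documents do not support them.

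- **That most such pregnancies are missed.** Counting conceptions to day +10 gives L/(L + 10), or 50% to 74% for L of 10 to 28 days. That count includes conceptions well after the roughly 48-hour exposure period.
- **That Section 10.3.3 makes later capture impossible.** The open-ended 24-hour rule contradicts this.
- **That withdrawal after a positive test removes cases from follow-up.** Section 10.3.3 anticipates withdrawal and still requires the investigator to follow the pregnancy to outcome. Section 4.4.3 also applies only where the Medical Monitor or site judges that safety is affected. What remains is a conflict of instructions, not a shown loss of follow-up.

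**Conclusion.** The point holds as a gap in the written collection rule. Collection closes at day 10, no test follows the last pre-dose test, and the study continues for a further 40 to 88 days, so a pregnancy exposed to the last dose can be recognised outside the stated window. Under the assumptions above, 17% to 67% of exposed pregnancies missed by the last test would be recognised late. This rests on an assumed lag, uniform conception dates and exposure ending at day +2.

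In absolute terms the effect is small. The SAP introduction reports termination at about twenty participants, and no effectiveness endpoint is touched. However, the SAP now focuses on safety, and its safety section names no pregnancy summary, so nothing in the analysis plan makes up for incomplete collection.

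The two conflicts need no assumption. The positive-test rule in Section 7.3.1 does not agree with Sections 4.4.3 and 10.3.3. The 10-day contraception limit in Sections 3.1 and 9.2.3.4 does not agree with Sections 7.1.1 and 11.1.

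**What to change.** In Section 10.3.3, extend data collection to any pregnancy the site learns of from Visit 0 through Study Termination. Add any pregnancy learned of later whose estimated conception date is on or before day 10 after the last session. Ask about pregnancy at the existing outcome site visit (V14 in the 2-session group, V18 in the 3-session group) and at Study Termination. No test is added.

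The cost is a wording change and one question at visits already scheduled. The small downside is that a few unexposed pregnancies will also be recorded. Where visits are already finished, sites can be asked retrospectively.

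Separately, the sponsor must reconcile Section 7.3.1 with Sections 4.4.3 and 10.3.3, so that a positive test leads to one stated course. It must also reconcile Sections 3.1 and 9.2.3.4 with Sections 7.1.1 and 11.1, so that contraception has one end date. This review does not say which rule should apply.
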